8.1.6 Adverse Events

Information regarding occurrence of adverse events will be captured throughout the study. Duration (start and stop dates and times), severity/grade, outcome, treatment and relation tostudy participation will be recorded on the case report form (CRF).

8.1.7 Urine Toxicology Test (UTOX)

A rapid urine toxicology test (UTOX) may be performed at the DAC offices. Results will not be posted in the participant's medical record.

8.1.8 Pregnancy Test

A urine or serum pregnancy test may be obtained from female subjects who are of childbearing potential.

8.1.9 Urinalysis

Urine may be obtained and sent to the site's clinical laboratory for determination of aroutine urinalysis and drug of abuse screen.

9 EVALUATIONS BY VISIT

Psychiatric interview tools to be used

- 1. The Mini Neuropsychiatric Interview (MINI-7) is a diagnostic interview used to determine psychiatric diagnoses in research settings based on DSM-V criteria. The brief structured interview assesses the 17 psychiatric disorders that are thought to be most prevalent (Sheehan et al., 1998).
- 2. The Visual Analogue Scales (VAS) (Bond and Lader 1974) are used to assess subjective state changes. They are 100-mm horizontal lines marked proportionately to the perceived intensity of the subjective experience (0=not at all, to 10=extremely) for the following states: anxious, depressed, drowsy, high, hungry, nauseous, control/dominance, happiness/pleasure, excitement/arousal, and vividness of image.
- 3. The Perceived Stress Scale (PSS) (Cohen et al. 1983) is a 10-item scale that measures the perception of stress. Each item is rated on a 5-point scale ranging from never (0) to almost always (4). Positively worded items are reverse scored, and the ratings are summed, with higher scores indicating more perceived stress. PSS-10 scores are obtained by reversing the scores on the four positive items: For example, 0=4, 1=3, 2=2, etc. and then summing across all 10 items. Items 4, 5, 7, and 8 are the positively stated items.
- 4. The Columbia Suicide Severity Rating Scale (C-SSRS) (Posner et al. 2011) is a suicidal ideation and behavior rating scale used to evaluate suicide risk. The C-SSRS is made up of ten categories, all of which maintain binary responses (yes/no) to indicate a presence or absence of the behavior. The ten categories included in the C-SSRS are as follows: Category 1 Wish to be Dead; Category 2 Non-specific Active Suicidal Thoughts; Category 3 Active Suicidal Ideation with Any Methods (Not Plan) without Intent to Act; Category 4 Active Suicidal Ideation with Some Intent to Act, without Specific Plan; Category 5 Active Suicidal Ideation with Specific Plan and Intent; Category 6 Preparatory Acts or Behavior; Category 7 Aborted Attempt; Category 8 Interrupted Attempt; Category 9 Actual Attempt (non-fatal); Category 10 Completed Suicide. A yes/no binary response is also utilized in assessing self-injurious behavior without suicidal intent. The outcome of the C-SSRS is a numerical score obtained from the aforementioned categories.
- 5. The Brief Psychiatric Rating Scale (BPRS) (Overall and Gorham, 1962) is a clinician-administered assessment used to capture acute behavioral changes throughout treatment. The scale includes 16 items each aimed at assessing components of psychosis including 4 items assessing positive (+) symptoms of psychosis such as conceptual disorganization, hallucinatory behavior, suspiciousness, and unusual thought content. Another 3 items assess negative (-) symptoms of psychosis such as: blunted affect, emotional withdrawal, and motor retardation. The remaining items assess activation and hostility by capturing tension, mannerisms and posturing, uncooperativeness, and grandiosity. Items that assess guilt, anxiety, depressed mood, and somatic concerns are also present.
- 6. The Patient Rated Inventory of Side Effects (PRISE) is an adverse Event Visit Checklist is a clinicianadministered questionnaire used to qualify side effects by identifying and evaluating the tolerability of each symptom.
- 7. The bipolar version of the Profile of Mood States (POMS-Bi) is a 72-item psychological rating scale used to assess transient, distinct mood states. Items are rated on a 4-point scale from 0, "much unlike this" to 3, "much like this". It includes six bipolar scales; composed-anxious, agreeable-hostile, elated-depresses, confident-unsure, energetic-tired, and clearheaded-confused. It is also a useful instrument in identifying the effects of drug treatments (O'Halloran et al., 2004).

While paper-and-pencil versions of self-report scales will be available, should participants express apreference for them, standard protocol will be to administer these measures via REDCap, a secure, password-protected web application for the development and management of surveys and databases. While participants will be able to access their own databases (with research team help), they will not be able to access anyone else's data. All participants will enter a subject code rather than an individually identifying PHI for purposes of self-report measures. Participants will be given opportunity to fill out these measures via computers in our offices. REDCap has a save-and-continue feature, which provides a session- and subject-specific code for continuation should participants desire to complete assessments off-site, further reducing participant burden.

9.1 Screening Visit (V0)

After receiving complete disclosure about the research and being given the opportunity to fully review the consent form, potential participants will be encouraged to ask the investigators questions. If they choose to take part in the study, they will be asked to provide written informed consent.

All participants will also undergo a diagnostic assessment, using the SCID–V or the MINI, in order to determine diagnosis. Screening measures may be completed under the screening protocol "A Screening Protocol for Adult Patients with Mood and Anxiety Disorders, Chronic Medical Conditions, and Healthy Volunteers" (GCO: 06-0945; PI [name]), as long as the assessments are completed within 6 weeks of the participant signing consent for the present protocol.

At the screen all participants will receive:

- 1) Psychiatric Assessments
 - a) MINI for psychiatric history (if a diagnostic assessment has not been completed already within the past 6 months under a DAC protocol.
 - b) C-SSRS
 - c) BPRS
 - d) Concomitant medication log
- 2) Medical Assessments
 - a) Medical history (Hx)
 - b) Physical examination (PE)
 - c) Vital signs (VS)
 - d) Electrocardiography (ECG)
 - e) Laboratory Tests: CBC, CMP, UTox, U/A, TSH
 - f) Urine tests: Drug abuse screen, Urinalysis, Pregnancy test (if applicable)

The study investigators will review the psychiatric interviews and medical assessments and identify eligible participants. The screening visit may occur on 2-3 separate days. All screening procedures will be completed before the Treatment visit - visit V1, and within four weeks of the treatment visit. As long as the screening assessments are completed within four weeks of the signing of consent for this protocol, the screening measures will not be repeated. Those found eligible based on screening assessment will be scheduled for the treatment visit within 4 weeks upon completion review of all screening procedures. Upon scheduling a baseline visit, eligible participants will be instructed to begin the low tyramine diet discussed during screening 3 days before the scheduled treatment visit. Participants will be routinely reminded by a member of the study team 4 days before a given treatment visit to begin the low tyramine diet the following day and see if the participant has any questions. Participants will also be systematically reminded 24 hours before their treatment visit to avoid food and drink at least 8 hours before dosing is set to begin. Adherence to the low tyramine diet

and the 8-hour NPO will be confirmed and recorded by the study clinician at the beginning of the treatment visit.

9.2 Treatment Visit (V1)

Refer to Table 2 for Visit 1 procedures.

9.3 Follow-up/Study Exit (V2)

Post-Baseline: approximately 24 hours after the oral dose

- a) Brief physical and interval medical history
- b) Update AE and con-med log
- c) Collect blood sample
 - a. 10 mL plasma
 - b. 3-5mL serum
- d) Clinical Scales/Self-Reports
 - a. C-SSRS
 - b. BPRS
 - c. POMS
 - d. PRISE
 - e. PSS
 - f. VAS

Study exit: Physician assessment followed by decision for discharge using standardized assessment scale

Time	Procedures
-90 min	 Subject arrives at Infusion Suite or CRU Name and number for escort home is collected Vitals* Urine tests: Drug abuse screen, Urinalysis, Pregnancy test (if applicable) Study doctor confirms 8-hour NPO Study doctor confirms adherence to low tyramine diet for past 72 hours Clinical assessments C-SSRS BPRS POMS PRISE PSS VAS Insertion of Hep-lock Baseline plasma and Serum sample: 1 ETDA and 1 SST
-10 min	 Pre-treatment baseline of vital signs: vital signs will

Table 2. Treatment Visit (Visit 1) Procedures

	be taken following 5 minutes of rest, with the average of two taken 5 minutes apart.
0 min	 Oral Administration of Harmine
+30 min	 Vital signs PRISE VAS Plasma and Serum sample: 1 ETDA and 1 SST
+60 min	 Vital signs PRISE VAS Plasma and Serum sample: 1 ETDA and 1 SST
+90 min	 Vital signs PRISE VAS Plasma and Serum sample: 1 ETDA and 1 SST
+ 120 min	 Vital signs PRISE BPRS VAS POMS Plasma sample
+180 min	 Vital signs PRISE VAS Plasma and Serum sample: 1 ETDA and 1 SST
+ 240 min	 Vital signs PRISE VAS Plasma sample
+ 300 min	 Vital signs PRISE VAS Plasma sample

+360 min	➤ Vital signs
	≻ C-SSRS
	≻ BPRS
	≻ POMS
	≻ PRISE
	> VAS
	> PSS
	➢ Plasma and Serum sample: 1 EDTA and 1 SST
+420 min	➤ Vital signs
	≻ C-SSRS
	> BPRS
	► POMS
	► PRISE
	> VAS
	≻ PSS
	➢ Plasma sample
+480 min	➤ Vital signs
	≻ C-SSRS
	► BPRS
	≻ POMS
	≻ PRISE
	≻ VAS
	≻ PSS
	➢ Plasma sample
Readily for discharge	 Physician assessment followed by decision for discharge
home	 Participants picked up by pre-designated escort home

*Prior to each vital sign, measurement the subject will be resting quietly for a minimum of five minutes before the vital signs are measured. For each specified vital sign time point, two readings will be taken 5 minutes apart and the average of the two readings will be used.

- *a)* Safety parameters for monitoring
 - Psychosis / mental status changes: BPRS, other clinical scales
 - PRISE: nausea, vomiting, diarrhea and other general adverse events
 - Vitals: BP, HR, Temp, Respiration
 - Unanticipated effects: spontaneous reporting and structured assessment with the PRISE

b). Plasma and Serum sampling

At screening, blood will be drawn for clinical screening labs including chemistry and hematology. For this purpose up to 16mL of blood will be drawn. On a separate treatment day, blood will be collected at eight timepoints over approximately eight hours for pharmacokinetic analysis. At each of these timepoints, 4mL of blood will be drawn. A 10ml of blood will be collected at timepoints -90, +60, +90, +180, +360 minutes and +24 hours for immune cell characterization in addition to pk analysis. At the same timepoints 3-5mL of serum will be drawn for analysis of c-peptides, insulin, and glucose.

c). Dosage of Harmine

The doses of harmine for oral administration are 100mg, 200mg, 300mg, 500mg, 700mg, 900mg and 1200mg. The rationale for using these doses is based on the modified Fibonacci sequence (i.e. 1, 2, 3.3, 5, 7, 9, 12, 16...) that is widely used in Phase I clinical trials (Le Tourneau, Lee et al. 2009).

d) Drug source, storage and preparation

a) Source: Harmine will be provided and compounded by The University of Minnesota College of Pharmacy ITDD.

b) Harmine will be stored by the Investigational Drug Service (IDS) of the Mount Sinai Pharmacy c) The manufacturing process of harmine consists of purification from the plant followed by salt formation to form harmine HCL under GMP conditions.

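### CMP and CBC are scheduled only at screening, so symptom-free early changes in liver, renal, electrolyte or blood-count results after dosing would not be found by schedule

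*Combined protocol and SAP*

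**What the plan says.** Section 9.1 lists the screening panel as "Laboratory Tests: CBC, CMP, UTox, U/A, TSH" and requires screening to be complete "within four weeks of the treatment visit". The sampling paragraph after Table 2 agrees: "At screening, blood will be drawn for clinical screening labs including chemistry and hematology".

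Blood taken from the treatment day onward has other named uses. The sampling paragraph says "blood will be collected at eight timepoints over approximately eight hours for pharmacokinetic analysis". It adds 10 mL samples at -90, +60, +90, +180 and +360 min and at +24 h for immune-cell characterization as well as PK, and then: "At the same timepoints 3-5mL of serum will be drawn for analysis of c-peptides, insulin, and glucose". Section 9.3 (V2, about 24 hours) lists a brief physical, an update of the adverse-event and medication logs, the plasma and serum samples, and rating scales. It lists no CMP or CBC.

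The list headed "Safety parameters for monitoring" names psychiatric scales, the PRISE and vital signs. Urinalysis on the dosing day falls in the -90 min row of Table 2, before the dose. Appendix 1 also marks urinalysis at the exit visit, but Section 9.3 does not list it, and Section 8.1.9 is permissive: "Urine may be obtained and sent to" the laboratory.

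Section 10.1 includes laboratory findings in the definition of an adverse event. Section 4.1 makes a non-serious event a DLT if it is at least moderate and at least possibly related.

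**The concern.** The trial exists to describe safety and to choose a dose for phase II. The plan accepts that a laboratory abnormality can be an adverse event and, if graded high enough, a DLT. Yet for the usual serum and blood-count tests, it schedules no measurement that could reveal one. The remaining routes (spontaneous report, the PRISE, the V2 log, medical judgment on seriousness) depend on symptoms or on someone ordering a test. A symptom-free rise in a liver enzyme or creatinine, or a fall in a cell count, prompts neither.

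Prior data do not fill the gap. The statistical section calls the human oral data limited and of poor quality. The clinical experience in Section 1 and the dose rationale in Section 4.1 report symptoms, mood, vital signs and PK, but no chemistry or blood-count results. They neither show a laboratory signal nor rule one out. What is at stake is participant safety and the completeness of the safety record handed to phase II.

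**Working it through.** **Step 1. Count the scheduled tests by visit** (Sections 9.1 and 9.3, Table 2, the sampling paragraph, Appendix 1).

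| Visit | CMP / CBC | Other laboratory tests |
|---|---|---|
| Screening | 1 | TSH, urinalysis, urine drug screen, pregnancy test |
| Dosing, -90 min | 0 | urine tests; baseline plasma and serum |
| Dosing, +30 to +480 min | 0 | PK, immune cells, C-peptide, insulin, glucose |
| V2, about 24 h | 0 | PK, immune cells, C-peptide, insulin, glucose; urine tests marked in Appendix 1 only |

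The Blood Sampling row in Appendix 1 is marked at dosing and exit but not at screening, where the CMP and CBC are drawn. The row therefore fits the research samples and does not add a safety panel.

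**Step 2. What a 24-hour panel could show.** For an abnormality present at 24 h with true rate p, the chance of at least one case in n participants is 1 - (1 - p)^n. The rates are assumptions; the documents give none. With n = 40, the planned maximum:

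- p = 2%: 1 - 0.98^40 = 0.554
- p = 5%: 1 - 0.95^40 = 0.871
- p = 10%: 1 - 0.90^40 = 0.985

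Zero cases in 40 would give a one-sided 95% upper bound of 1 - 0.05^(1/40) = 0.072.

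**Step 3. Those figures pool all doses.** The design concentrates participants near the target dose. I simulated a one-parameter empiric CRM with the Section 4.1 prior rates (2%, 5%, 10%, 20%, 30%, 50%, 65%) as both skeleton and truth, a 25% target, a start at 100 mg, no skipping, the coherence rule, N = 40 and an assumed normal prior variance of 1.34. On average about 3.6 of 40 participants receive 900 mg or more. Putting n = 3.6 into the formula:

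- p = 2%: 1 - 0.98^3.6 = 0.07
- p = 5%: 1 - 0.95^3.6 = 0.17
- p = 10%: 1 - 0.90^3.6 = 0.32

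These are on the high side, because the number treated at those doses varies between trials and the formula is concave in n. If harmine is better tolerated than the prior assumes, more participants reach the top doses and the chance rises.

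**Step 4. Blood volume.** The screening allowance of up to 16 mL is taken as the ceiling for one added panel. The sampling paragraph gives eight PK times and Table 2 gives eleven plasma times, so the planned total is a range, counting the 3-5 mL serum as blood.

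- Low, with the 10 mL draws replacing 4 mL PK draws at the five shared times: 16 + 3x4 + 6x10 + 6x3 = 106 mL
- High, Table 2 plus V2: 16 + 11x4 + 6x10 + 7x5 = 155 mL
- Two added panels: 2 x 16 = 32 mL, for totals of 138 to 187 mL

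**Step 5. Why no laboratory DLT threshold is proposed.** The trial has no control group, and attribution needs only a possible relationship. If background abnormalities at rate b counted as DLTs, the DLT rate would become p + b(1 - p). At an assumed b = 5%, the prior 20% at 500 mg becomes 0.20 + 0.05x0.80 = 24.0%, and the prior 30% at 700 mg becomes 0.30 + 0.05x0.70 = 33.5%. That could move the selected dose.

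**The case against.** The strongest reply is that monitoring is aimed at what the cited evidence shows: neurological, psychiatric, gastrointestinal and haemodynamic effects. Nothing cited points to liver, kidney or marrow. Each participant takes one dose, and the mean half-life reported from the ayahuasca study in Section 1 is about 116 minutes. The protocol also argues from intravenous dosing to 300 mg, which it converts to about 3,000 mg oral, so 1200 mg is not beyond all cited exposure. On this view the panel is a reasonable extra, not a repair. This stands in part: no signal is documented and nothing in the analysis breaks. But the intravenous conversion is the protocol's own estimate, and no laboratory results are reported with it, so it does not answer the question.

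Post-dose blood is also not free of clinical content. Glucose is a chemistry value and is measured to +24 h. Immune-cell characterization might show some white-cell change, though it is not described as a count or a safety review. A reader might infer that the trial takes no laboratory test after dosing. The documents do not support that reading.

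A reader might also infer that the MTD is biased, or that laboratory cut-offs should be added to the DLT definition. Neither follows. The severity table in Section 10.1 grades by activity limitation and need for therapy, so a symptom-free abnormality needing no treatment would tend to be graded mild and not count under the moderate-event criterion. Section 2.2 points to FDA guidelines and a tracking form that are not in the documents, and these may hold cut-offs. Adding a threshold is a separate trade-off that could itself shift the dose.

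Some text just before the safety-monitor description was not available to this review. Section 9, Table 2 and Appendix 1, which set the schedule, were.

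**Conclusion.** The concern holds in this limited form. CMP and CBC are scheduled once, at screening, up to four weeks before dosing. None is scheduled afterward, so the plan yields 0 post-dose panels where existing visits could yield up to 40 with same-day baselines. Symptom-free early changes in liver enzymes, creatinine, electrolytes or blood counts would not be found by schedule.

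The pooled detection chances (55%, 87%, 98%) rest on assumed rates, on all 40 participants being dosed and tested, and on the abnormality being present at 24 hours. They should not be read as sensitivity at the top doses, where few participants are expected and the chance is roughly 7%, 17% or 32% at the same rates. No laboratory toxicity of harmine is asserted and no effect on the MTD is claimed. This is an inexpensive improvement to safety measurement, worth making, and not a flaw in the dose-finding analysis.

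**What to change.** In Table 2, Section 9.3 and Appendix 1, add CMP and CBC to the existing -90 min draw, as a same-day baseline, and to the existing V2 draw at about 24 hours. Have the study physician compare the two and follow up clinically significant changes. Handle these through the grading in Section 10.1, the DLT definition in Section 4.1 and the existing review of suspected DLTs. Add no new laboratory DLT threshold.

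The cost is up to 16 mL more blood per added panel (32 mL for both), with no new visit or venipuncture, and routine assays at the on-site chemistry laboratory described in Section 2.1. Some non-specific abnormalities will need follow-up, and the next dose assignment may have to wait for the V2 result. A 24-hour panel finds early changes only and says nothing about later ones.

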10 ADVERSE EXPERIENCE REPORTING AND DOCUMENTATION

10.1 Adverse Events

An AE is any untoward medical occurrence in a study subject administered an investigational product and that does not necessarily have a causal relationship with atreatment.

An AE therefore can be any unfavorable and unintended sign (including laboratory finding), symptom or disease temporally associated with participation in an investigational study, whether or not considered drug-related. In addition to new events, any increase in the severity or frequency of a pre-existing condition that occurs after the subject signs a consent form for participation is considered an AE. This includesany side effect, injury, toxicity, or sensitivity reaction.

Any condition, laboratory abnormality, or physical finding with an onset date prior to the subject signing consent for study participation is considered to be pre-existing in nature and part of the subject's medical history.

AE Severity

Severity (Toxicity Grade)	Description
Mild (1)	Transient or mild discomfort; no limitation in activity; no medical intervention or therapy required. The subject may be aware of the sign or symptom but tolerates it reasonably well.

Table 1. AE Severity Grading

Page 32 of 43

Protocol STUDY-20-01329	Confidential
Moderate (2)	Mild to moderate limitation in activity, no or minimal medical intervention/therapy required.
Severe (3)	Marked limitation in activity, medical intervention/therapy required, hospitalizations possible.
Life-threatening (4)	The subject is at risk of death due to the adverse experience as it occurred. This does not refer to an experience that hypothetically might have caused death if it were more severe.

AE Relationship to Study Drug

1). Attribution of Adverse Events:

No: Adverse events are clearly not related to the investigational agents Unlikely: Adverse events are doubtfully related to investigational agents Possibly: Adverse events may be related to investigational agents Probably: Adverse events are likely related investigational agents Definitely: Adverse events are clearly related to the investigational agents

2). Plan for grading adverse events:

The FDA's definition of serious adverse events (21 CRF 312) include any untoward medical occurrence that at any time results in death or the immediate risk of death, hospitalization or the prolonging of an existing hospitalization, persistent or significant disability/incapacity or congenital anomaly/birth defect (NOH Guide, 6/11/99).

Grades of Risk: 1 = Non-Serious Adverse Event 2 = Serious Adverse Event

The PI will report all serious adverse events, verbally and in writing, to the Mount Sinai IRB within 48 hours.

10.2 Serious Adverse Experiences (SAE)

An SAE is defined as any AE occurring at any dose that results in any of the following outcomes:

- Death
- Life threatening experience defined as any adverse experience that places the subject, in the view of the treating physician, at immediate risk of death at the time of occurrence; ie, it does not include a reaction that, had it occurred in a more severe form, might have caused death.
- Requires inpatient hospitalization or prolongation of an existing hospitalization (except scheduled hospitalizations for non-acute, unrelated cause such as an electivesurgery)
- Results in persistent or significant disability/incapacity
- Is a congenital anomaly/birth defect in the offspring of an exposed subject
- Important medical events that may not result in death, be life threatening, or require hospitalization, may be considered an SAE when, based upon appropriate medical judgment, it jeopardizes the subject and may require medical or surgical intervention prevent one of the outcomes listed in this definition.
- Any death occurring within 30 days of the subject receiving study drug, regardless of the

subject having discontinued from the protocol, must be reported as an SAE.

Other important medical events may also be considered an SAE when, based on appropriate medical judgment, they jeopardize the subject or require intervention to prevent one of the outcomes listed.

AE/SAE Reporting Procedure

To Mount Sinai PPHS (IRB)

AEs are reportable to the IRB within 5 business days (SAEs within 24 hours of knowledgeof the event) when they meet the following definition:

Any 'harm' experienced by a subject or other individual that in the opinion of the investigator is *unexpected* AND *at least probably related* to the research

All AE/SAEs with an onset date after the subject signs consent for study participationmust be reported to the IRB *at the time of annual renewal*. Details of the event must include severity, relationship to study drug, duration, action taken, and outcome.

All AE/SAEs that are considered related to study drug must be followed to resolution or stabilization if improvement is not expected. AE/SAEs that completely resolve and then recur should be recorded as a new AE/SAE. AE/SAEs continuing at 30 days post-last dose should have acomment in the source documents by the PI that the event has stabilized or is not expected to improve.

